### **3.2 Dosing Rationale**

Although no serious adverse events are anticipated with the doses we propose, the first cohort of subjects will be a run-in of three patients receiving 50mg suppositories. If no mucosal or systemic adverse events are reported, we will proceed with 200mg dosing.

A five-day dosing regimen with a single dose of 200 mg per 24-hour period is selected based on the clinical toxicology and pharmacology database from anti-malarial and cancer trials as well as the performance data presented on the inhibition of HPV infected cells *in vitro* and *in vivo*. We anticipate that intra-vaginal administration of 200 mg Artesunate suppositories to the cervix will provide a local drug concentration well above IC50 of HPV-infected cells. Based on our experimental experience in nonclinical studies, we plan to assess more than one 5-day treatment cycle to explore potential dosing regimens suitable for subsequent phases of clinical studies.

The doses selected for this study are 50 mg and 200 mg. A dose level of 200 mg is equivalent to  $\leq 4\text{mg/kg}$  based on a minimum body weight of 50 kg as a subject inclusion criterion. The proposed dose level should be extremely safe as it is well within WHO recommended pre-referral dose for parenteral Artesunate treatment of severe malaria in young children; that is a single dose of 10mg/kg body weight. The proposed dosing regimen also resembles WHO recommended multi-day dosing regimen for adults and children with severe malaria upon hospitalization; that is 2.4mg/kg IV or IM TID on day 1 (or 7.2 mg/kg) and continued daily dosing at 2.4mg/kg for a total of 7 days [43]. Due to the rapid rate of elimination *in vivo*, negligible systemic accumulation of Artesunate or DHA metabolite is expected over multi-day dosing, especially in the case of local administration.

In summary, local intravaginal administration of Artesunate as a suppository at the highest dose in this study, 200 mg or approximately  $\leq 4\text{ mg/kg}$  is not expected to cause any systemic toxicity. Although no serious adverse events are anticipated with the proposed doses, dose escalation will only occur if no mucosal or systemic adverse events are reported in the first cohort of three subjects who receive the lowest dose. Subjects will be monitored for any unexpected adverse events locally and systemically.

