#### **5.0 RATIONALE FOR CLINICAL TRIAL DESIGN**

This trial is a prospective, open, dose-escalation study of topical Artesunate, formulated as a suppository, administered intravaginally, prior to standard therapeutic resection of the squamocolumnar junction at study week 15. An initial dose cohort of 3 subjects will receive intravaginal Artesunate for one 5-day treatment cycle. Based on clinical experience with Artesunate, we expect that absorption in the cervical mucosa, which is stratified squamous epithelium, will be less than what is observed with rectal administration, which is a single layer of glandular epithelium. Because cervical stroma is much less vascularized than colorectal stroma, we also expect significantly lower systemic levels of Artesunate in subjects receiving intravaginal dosing. The goal of topical administration is to achieve local, mucosal distribution of study drug, as opposed to systemic levels.

If we do not observe untoward side effects, including mucosal excoriation, in the first dose cohort, we will proceed with dose-escalation. The subsequent cohort will undergo two cycles of treatment, spaced at 2-week intervals. The final cohort will undergo a total of three cycles of treatment, spaced at 2-week intervals. All subjects will undergo an interval colposcopic exam at study week 6. At week 15, if there is still a colposcopically detectable lesion, subjects will undergo standard therapeutic resection. If no lesion is obvious, a biopsy will be taken at the site of the original lesion. The cohort receiving the fewest cycles of Artesunate, and showing therapeutic effect will be expanded (see Section 12 for details). At each vaginal exam, cervical swabs will be obtained and cryopreserved. Peripheral blood will be obtained by venipuncture at baseline, and at study weeks 5, 15, and 28, 41, and the postop visit, and will be cryopreserved for assessment of biomarkers.

This clinical cohort, healthy subjects with colposcopically-directed, biopsy-confirmed CIN2/3, was selected for safety reasons. The study protocol window (15 weeks), is within the standard of care. In pregnant women who have a cervical HSIL, the standard of care is to follow colposcopically until postpartum [7]. We and others have reported that the probability that CIN2/3 will progress in this timeframe is essentially zero [63]. In fact,

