## **8.0 STUDY DESIGN**

Prior to enrollment, patients referred for evaluation of an HSIL pap smear will undergo a full colposcopic evaluation, with biopsy confirmation. Clinical, histopathologic, virologic, and immunologic parameters will be assessed longitudinally in each study participant, as outlined below. The trial is a dose-escalation design, with a run-in cohort to assess the likelihood of mucosal irritation.

These serial assessments will directly parallel those obtained in the currently open CIN2/3 cohort study (JHMI JCCI# 99-08-27-04). Those patients who have measurable disease after biopsy will be eligible for study participation.

Cervical tissue specimens obtained as routine diagnostic and therapeutic specimens will be analyzed to characterize local tissue immune response. Diagnostic biopsies obtained at initial colposcopy will be used to confirm the diagnosis of CIN2/3. The initial diagnostic biopsy specimens will also be characterized in terms of type and quantitation of inflammatory cell infiltrates. Immunocytochemical techniques will be used to determine presence and numbers of macrophages, dendritic cells, T cells, B cells, and NK cells. We will also use standard staining techniques to detect cleaved caspase 3. As tissue availability permits, the specimens will also be analyzed for other immune cells. We will be comparing tissue profiles with those obtained on circulating PBLs in our study population. In the post-suppository administration, therapeutic LEEP/cone biopsy specimens, markers of local tissue immune response will be similarly characterized and quantitated. [name] will review all of the histologic slides.

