### **11.2 Dosage and Administration**

At each dosing visit, after a negative pregnancy test is confirmed, the study physician or nurse will provide five daily vaginal suppositories. During that visit, the subjects will be trained in the vaginal insertion of Artesunate suppositories followed by a tampon, and instructed to administer all daily doses at home at bedtime.

The first 3 study subjects (healthy volunteers with CIN2/3) will receive five (5) daily suppositories that contain 50 mg Artesunate. The 50 mg dose (or  $\leq 1\text{mg/kg}$  for subjects weighing 50kg at minimum) is considerably lower than that used when the anal suppository is intended to deliver a systemic dose of drug for malaria – the 50 mg suppository is recommended by WHO for pediatric care. If no local irritation or systemic toxicities observed in the first 3 patients at 50mg, the dosage will escalate to 5 daily doses of 200 mg per day for the remainder of study enrollments (see treatment cohort table).

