### 11.5 Management of Toxicities

All local reactions will be considered causally related to administration of the suppositories. Causality of all other adverse events will be assessed individually. We will follow up subjects with non-serious adverse events until symptoms end. Those with

related serious adverse events will be followed until resolved, until no further improvement is expected, until a non-study antitumor therapy is initiated, or for 30 days after last study treatment, whichever comes first (with the exception of neuropathy, which must be followed until resolution to  $\leq$  grade 1 or until stable for 60 days).

Outcome will be assessed as

- 1=Recovered
- 2=Recovered with sequelae
- 3=Ongoing at subject study conclusion
- 4=Died
- 5=Unknown

Any serious study events that are unexpected and related to the study drug or procedure occurring during the period starting from day of administration of the first dose of Artesunate suppository to each subject and ending at the last study visit for that subject (i.e., scheduled LEEP or cone excisional biopsy procedure), will be reported by the principal investigator.

Subjects who become pregnant during study will be required to discontinue drug. Subjects removed from the study prior to week 15 will be replaced in the dose cohort. Although not considered an adverse event, pregnancy will be reported in the same way. Whenever possible, a pregnancy should be followed to term, and the status of mother and child reported. The Pregnancy Notification form will be sent by sites to the study sponsor ([name]) within 48 hours of discovery. Whenever possible, the Follow-up Pregnancy Outcome Form will be filled after delivery.

Significant local inflammation will be treated symptomatically with cold packs and oral analgesics. Local infection or ulceration will be treated with routine wound care and antibiotics if necessary.

Subjects will be given diary cards to record local and general signs and symptoms most likely to occur at home. The diary cards will be collected, signs and symptoms verified, and inserted into the CRF at each subsequent visit. Subjects will be monitored at regular intervals to ensure that all adverse events are recognized, documented, and treated. Patients will be educated to contact medical staff should they feel that an adverse event has occurred at a time when they are not scheduled for follow-up monitoring and will have access to medical staff to follow up on any such concerns.

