### **11.8 Definition of Dose-Limiting Toxicity**

A dose-limiting toxicity is defined as any grade 3 toxicity in any organ system, or grade 2 or higher allergic reaction/hypersensitivity reaction (allergy/immunology), as delineated in CTCv4.0.

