## **12.0 STATISTICAL CONSIDERATIONS**

### **12.1 Study Design/Endpoints/Accrual**

The primary statistical outcome of the trial is safety. The treatment groups will be filled sequentially in a non-blinded manner. Study dropouts will be replaced.

The dose escalation algorithm is described as follows (see Table 4 for dose levels to be tested):

1. A run-in cohort of three patients will be treated with one 5-day cycle of 50mg vaginal suppositories. If no patient has a DLT observed by the cervix check visit after the last suppository, the trial will proceed to the next level.
2. A cohort of 9 patients will be enrolled and treated with one 5-day cycle of 200mg vaginal suppositories. If no patient has a DLT observed by the cervix check after the last suppository, the dose level will be considered tolerable and the trial will proceed to the next level.
3. If exactly one of the 9 patients has a DLT by Week 1-2 after the last suppository, three more patients will be enrolled and treated at the current dose level. If none of the three patients has a DLT by the cervix check after the last suppository, the current dose level will be considered safe and dose will be escalated.
4. If two or more of the 9 or 12 patients have a DLT observed by Week 1-2 cervix check, dose escalation will be stopped. The current dose level will be considered unsafe.
5. A cohort of 9 patients will be enrolled and treated with 2 cycles of 200 mg vaginal suppositories, at 2-week intervals. If no patient has a DLT observed in Cohorts II and III, then the dose level will be considered safe, and the dose will be escalated.
6. A cohort of 9 patients will be enrolled and treated with 3 cycles of 200 mg vaginal suppositories, at 2-week intervals. If no patient has a DLT observed by the cervix check after the last suppository, then the dose level will be considered safe.

With the dose escalation algorithm, there will be less than 9% probability to escalate to the next higher dose level if the DLT rate for the current dose level is 30%.

The maximum sample size for dose escalation is 39. Based on our experience in investigator-initiated therapeutic trials in this patient population at this institution, our anticipated accrual rate is 20-25 patients per year.

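### A mild local reaction in the run-in both blocks and permits the step from 50 to 200 mg; step 5 leaves one path without an outcome, and the escalation probability is 9.4%, not below 9%

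*Combined protocol and SAP*

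**What the plan says.** The condition for leaving the 50 mg run-in appears in four places.

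- Section 12.1, step 1: "If no patient has a DLT observed by the cervix check visit after the last suppository, the trial will proceed to the next level". Section 11.8 supplies the threshold: "A dose-limiting toxicity is defined as any grade 3 toxicity in any organ system", or an allergic or hypersensitivity reaction of grade 2 or higher.
- Section 3.2: "dose escalation will only occur if no mucosal or systemic adverse events are reported in the first cohort of three subjects".
- Section 11.2: "If no local irritation or systemic toxicities observed in the first 3 patients at 50mg, the dosage will escalate".
- Section 5.0: "If we do not observe untoward side effects, including mucosal excoriation, in the first dose cohort, we will proceed with dose-escalation".

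Section 8.0 gives the purpose of the run-in: "The trial is a dose-escalation design, with a run-in cohort to assess the likelihood of mucosal irritation".

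For the 200 mg cohorts, 12.1 sets a 9+3 rule. Under step 2, 0 DLTs in 9 moves the trial on at once. Step 3 reads "If exactly one of the 9 patients has a DLT by Week 1-2 after the last suppository, three more patients will be enrolled", and the level passes if none of the three added patients has a DLT. Under step 4, two or more DLTs in 9 or 12 stop escalation. Step 5, for cohort III, makes the next escalation depend on there being no DLT in cohorts II and III. Section 12.1 then gives a maximum of 39 patients for escalation, and a probability below 9% of escalating from a level whose true DLT rate is 30%.

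**The concern.** Safety is the primary outcome. These rules decide whether the dose rises fourfold and whether a regimen is called safe, so each possible result should lead to one decision.

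In the run-in, the conflict falls on grade 1 and 2 local reactions, such as mild burning or erythema. Section 4.1 names local irritation as a potential risk, and 7.1 lists such symptoms among the primary safety outcomes. Investigators who see one such event cannot follow both 3.2 and step 1. Section 15.1 bars departures from the protocol without prior IRB approval, so either choice departs from some protocol text.

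Step 5 raises a similar problem later in the trial, but only after a single DLT in cohort II. The probability statement is the only operating characteristic given for the safety design, and it is stated as a strict upper bound.

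**Working it through.** **1. The plan's own figures.** Inputs from 12.1: DLT rate p = 0.30, first stage of 9, second stage of 3.

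The maximum of 39 reproduces as 3 + (9+3) + (9+3) + (9+3). It therefore requires the 9+3 rule in each of cohorts II, III and IV.

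A figure below 9% comes from treating 12 patients in every case and allowing at most one DLT:

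- 0.7^12 + 12(0.3)(0.7^11) = 0.0138 + 0.0712 = 0.0850, or 8.5%.

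This is a likely source, but it is not the written rule, because step 2 escalates on 0 of 9 without treating three more. The written rule gives:

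- P(0 of 9) = 0.7^9 = 0.0404
- P(1 of 9) × P(0 of 3) = 9(0.3)(0.7^8) × 0.7^3 = 0.1556 × 0.343 = 0.0534
- Sum = 0.0937, or 9.4%.

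The difference, 0.0937 − 0.0850 = 0.0087, is the chance of 0 of 9 followed by two or three DLTs in the three patients whom the written rule never enrols: 0.0404 × 0.216.

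The run-in follows a different rule. Under step 1, the chance of 0 of 3 at the same rate is 0.7^3 = 34.3%.

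**2. The run-in trigger.** Outcomes among the three patients at 50 mg:

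| Worst event | 12.1 step 1 with 11.8 | 3.2 | 11.2 |
|---|---|---|---|
| None | proceed | proceed | proceed |
| Grade 1–2 local reaction, non-allergic | proceed | do not proceed | do not proceed |
| DLT | condition not met | do not proceed | do not proceed |

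Only the middle row conflicts. Section 3.2 makes the absence of events a necessary condition, while step 1 makes the absence of a DLT a sufficient one, so the contradiction with 3.2 is strict. Section 11.2 blocks on its ordinary reading, although it lacks the word *only*. Attribution offers no way out: 3.2 has no relatedness qualifier, and 11.5 says "All local reactions will be considered causally related to administration of the suppositories".

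The protocol gives no event rate. As an illustration, assume that no run-in patient has a DLT and that each has probability m of an adverse event below DLT level. Section 3.2 and step 1 then disagree with probability 1 − (1 − m)^3:

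- m = 0.1: 27%
- m = 0.3: 66%
- m = 0.5: 88%

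**3. Step 5.** Suppose cohort II has 1 of 9 and then 0 of 3. Step 3 calls the level safe and cohort III opens.

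- Cohort III has 0 of 9: step 5 is not met because of the cohort II DLT, step 3 does not apply, and step 4 does not stop escalation. No outcome is stated.
- Cohort III has 1 of 9 and then 0 of 3: read per cohort, as the maximum of 39 implies, step 3 escalates.

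The cleaner result is thus the one left undefined. Its probability, counted from entry to cohort II with the same DLT rate p in both cohorts, is 9p(1 − p)^11 × (1 − p)^9. At assumed p = 0.01, 0.05 and 0.10 this is 7%, 16% and 11%.

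**The case against.** The sponsor could say that 3.2 is rationale and that the statistical section governs. But 11.2 is an operative dosing section, and the protocol states no order of precedence. The sponsor could also say that mild run-in events would be seen: 12.4 schedules a toxicity review after the first treatment group, and 14.0 provides bi-weekly data review and a Safety Monitoring Committee. That is true, and holding at 50 mg is a safe default. These safeguards lower the risk, but none of them says which threshold applies.

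On step 5, the two cohorts share the 200 mg dose, so a joint look at both could be deliberate caution. That remains possible. The missing outcome would then still have to be written down. On the probability, the excess over 9% is 0.37 percentage points and changes no decision. That also stands.

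Four stronger inferences are tempting, and the documents do not support them.

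- *Step 1 lets the dose rise after a DLT.* No wording permits this; the conflict is confined to events below DLT level.
- *Section 5.0 also contradicts step 1.* Its reference to untoward side effects carries no grade and can be read alongside a DLT threshold.
- *The 34.3% shows the stated bound to be wrong almost fourfold.* The sentence most naturally describes the 9+3 rule, and 34.3% assumes that step 1 governs the run-in. Under 3.2 or 11.2 the chance could only be equal or lower. This is a point about scope.
- *Section 11.9 halts the trial at the first grade 3 event.* Its first sentence does not say what is stopped, but the two-event accrual suspension that follows, and step 3, favour a subject-level reading.

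**Conclusion.** The point holds and should be fixed. Its weight rests on the run-in, where 3.2 and 11.2 conflict with step 1 for any grade 1 or 2 non-allergic local reaction. That conclusion comes from the text alone. The 27%, 66% and 88% only show how often the conflict could arise under assumed event rates.

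The step 5 gap is real but conditional. It needs exactly one DLT among 12 patients in cohort II, and 5.0 does not expect DLTs. The 7%, 16% and 11% also rest on assumed rates.

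The probability is a small numerical correction: 9.4% against a stated bound of 9%, using the protocol's own 30% DLT rate. As written, it applies without ambiguity only to the move from cohort II to cohort III. It extends to cohort III once step 5 is settled on a per-cohort basis. There is no escalation from cohort IV, where the same figure is the chance of calling the regimen safe. None of this shows that the escalation scheme itself is unsafe.

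**What to change.** 1. Put one run-in criterion in 3.2, 11.2 and 12.1 step 1, and align 5.0 with it. Whether it is any local or systemic event, a grade threshold or a DLT is for the sponsor and investigators to choose. Until then, follow the stricter wording of 3.2 and 11.2.
2. State that steps 3 and 4 apply separately to cohorts II, III and IV, and reword step 5 to refer to cohort III alone. If pooling cohorts II and III is intended, keep it and state what happens when cohort II had one DLT.
3. Restate the probability as: *about 9.4% for escalating from cohort II or III (and for declaring cohort IV safe) under the 9+3 rule at a 30% DLT rate; it does not apply to the three-patient run-in.* If pooling is kept, limit the figure to the step from cohort II and compute cohort III separately.
4. Optionally, say in 11.9 whether its first sentence stops dosing for the subject or stops the trial.

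The cost is amendment wording and one figure, with no new procedures or patients. With the per-cohort wording the escalation maximum stays at 39. The Synopsis total of 30 equals the planned 3 + 9 + 9 + 9. This change neither alters that total nor reconciles it with the maximum.

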### **11.9 Early stopping rules**

Because this is a pilot study evaluating tolerability of a new intra-vaginal treatment, the stopping rule for safety is the presence of Grade 3 toxicity in any organ system, or grade 2 or higher allergic/hypersensitivity reaction as delineated in CTCAEv4.0. In the event of two identical unexpected related treatment-related Grade 3 toxicities, accrual will be suspended pending further review.

Subjects who become pregnant during study will be required to discontinue drug. Although not considered an adverse event, pregnancy will be reported in the same way. Whenever possible, a pregnancy should be followed to term, and the status of mother and child reported. The Pregnancy Notification form will be sent by sites to the study sponsor ([name]) within 48 hours of discovery. Whenever possible, the Follow-up Pregnancy Outcome Form will be filled after delivery.

Finally, if there is evidence of disease progression at the interval visit regardless whether the progression may or may not be associated with Artesunate, patients will undergo resection at that point.

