At the end of dose escalation phase, one dose will be selected for the expansion phase from dose levels II-IV that are considered safe. In general, the lowest dose level with significant within subject decreases in viral load (from baseline at Week 15) and lesion clearance to CIN1 or less will be selected (see Section 12.2 for details). If none of the safe doses achieve significance for decrease in viral load and lesion clearance, a decision will be made based on the totality of safety and efficacy profiles of the dose levels considered safe.

A cohort of 12 patients will be enrolled and treated at the selected dose level at the expansion phase to further evaluate the safety and efficacy of Artesunate.

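### Section 12.1 step 5 does not fit step 3: after Cohort II passes with one DLT, a clean Cohort III meets no decision rule; the stated escalation probability is also slightly too low

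*Combined protocol and SAP*

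**What the plan says.** Section 12.1 sets out six steps. A run-in of three patients at 50 mg is followed by Cohorts II, III and IV, each of 9 patients at 200 mg, with one, two and three cycles.

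- **Step 2:** Cohort II with 0 of 9 DLTs goes on to the next level.
- **Step 3:** "If exactly one of the 9 patients has a DLT by Week 1-2 after the last suppository, three more patients will be enrolled". If none of the three added patients has a DLT, "the current dose level will be considered safe and dose will be escalated".
- **Step 4:** two or more DLTs among the 9 or 12 patients stop escalation.
- **Step 5 (Cohort III):** "If no patient has a DLT observed in Cohorts II and III, then the dose level will be considered safe", and escalation follows.
- **Step 6 (Cohort IV):** gives only the outcome with no DLT.

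The section then states two figures. For a 30% DLT rate, "there will be less than 9% probability to escalate to the next higher dose level". On size: "The maximum sample size for dose escalation is 39". Afterwards, "one dose will be selected for the expansion phase from dose levels II-IV that are considered safe".

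Section 11.8 defines a DLT as any grade 3 toxicity, or an allergic or hypersensitivity reaction of grade 2 or higher. Section 11.9 names the same events in its first sentence: "the stopping rule for safety is the presence of Grade 3 toxicity in any organ system", with the same allergic criterion added. Its second sentence reads: "In the event of two identical unexpected related treatment-related Grade 3 toxicities, accrual will be suspended pending further review".

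**The concern.** Step 3 treats one DLT in 12 as acceptable. Step 5 asks for none across Cohorts II and III together. Once Cohort II has used the allowance in step 3, step 5 cannot be satisfied by anything that happens in Cohort III, and step 5 has no other branch.

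Safety is the primary statistical outcome, and only levels judged safe may go forward to expansion. In this situation nine women would receive two cycles without a DLT, yet no written rule would call their level safe or open Cohort IV. A worse Cohort III result would have a route to passing. The escalation rule would have to be settled once the DLTs in an unblinded trial were known.

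Separately, the plan gives one operating characteristic for the rule, so that figure should match the rule.

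**Working it through.** **1. Maximum sample size.** The run-in has 3 patients. If each of Cohorts II, III and IV can expand from 9 to 12, the maximum is 3 + 12 + 12 + 12 = 39, which is the plan's figure. If steps 3 and 4 belonged to Cohort II alone, it would be 3 + 12 + 9 + 9 = 33. So 39 needs the 9+3 rule at all three levels.

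**2. The plan's escalation probability.** For DLT rate p, with independent patients, a level passes with probability

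(1−p)^9 + 9p(1−p)^8 × (1−p)^3.

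At p = 0.30 this is 0.0404 + 0.0534 = 0.0937, or 9.4%, against a stated value below 9%. The probability of at most one DLT in 12 is 0.0850, which would fit the statement. That calculation assumes all 12 patients are always treated, whereas the rule passes a level at 0 of 9 without adding three.

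**3. Outcomes of Cohort III after Cohort II has passed with 1 of 12.** Steps 3 and 4 are read as applying to whichever level is current.

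| Cohort III result | Rule that applies | Decision |
|---|---|---|
| 0 of 9 | none: step 5 has already failed, step 3 needs exactly one, step 4 needs two or more | not stated |
| 1 of 9, then 0 of 3 | step 3 | safe, escalate |
| 1 of 9, then 1 or more of 3 | step 4 | stop |
| 2 or more of 9 | step 4 | stop |

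The best result is the only one without a decision.

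**4. How often this arises.** The DLT rates here are assumptions. They are taken as equal in Cohorts II and III, with the run-in already passed. Low rates are included because section 5.0 expects no dose-limiting toxicities.

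- Cohort II passes with one DLT: P1 = 9p(1−p)^11.
- Cohort III is clean: P0 = (1−p)^9.
- State without a rule: P1 × P0.

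| p | P1 | P0 | P1 × P0 |
|---|---|---|---|
| 1% | 0.081 | 0.914 | 0.074 |
| 2% | 0.144 | 0.834 | 0.120 |
| 5% | 0.256 | 0.630 | 0.161 |
| 10% | 0.282 | 0.387 | 0.109 |

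**5. With the 9+3 rule applied separately in Cohorts II and III**, Cohort IV opens with probability (P0 + P1)^2 = 0.988, 0.956, 0.785 and 0.449 at these four rates.

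**The case against.** The strongest reply is that the intent can be recovered. Steps 3 and 4 speak of the current level and of 9 or 12 patients, and 39 fits only a 9+3 rule at each 200 mg cohort. On that view, naming both cohorts in step 5 is a drafting slip. This is probably right and it decides the fix, but it does not make the text workable as it stands. Both cohorts receive 200 mg, so a reader could also take the phrase as a deliberate cumulative check.

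The consequence is also limited. The gap errs on the cautious side, since nothing written then permits Cohort IV. Cohort II remains safe under step 3 and eligible for expansion. Section 14.0 provides a Safety Monitoring Committee, and section 15.1 requires prior written IRB approval for any change, so investigators would not be free to improvise. All of this stands and limits the weight of the point.

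Two stronger readings are tempting.

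- A reader might infer that step 5 requires zero DLTs over both cohorts, so that any expansion in Cohort II or III blocks Cohort IV. The maximum would then be 3 + 9 + 9 + 12 = 33. But step 5 states a sufficient condition (if, not only if), and 33 contradicts the plan's 39.
- A reader might infer that the first sentence of section 11.9 stops the trial at a single DLT and so contradicts step 3. That sentence does not say what stops. Its companion sentence suspends accrual only after two identical events, and 39 could not be reached if one DLT ended the trial. This is an ambiguity, not an established contradiction.

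**Conclusion.** The inconsistency between steps 3 and 5 is real and can be read from section 12.1 alone. One DLT in 12 in Cohort II followed by none in 9 in Cohort III has no decision. The probability of that path is about 7% to 16% for DLT rates between 1% and 10%, assuming independent patients and the same rate after one and two cycles. A different rate with two cycles would change these figures but would not remove the gap.

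The stated escalation probability is wrong by a small amount: 9.4% for the rule as written, not below 9%. This changes no decision and needs only to be corrected.

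The wording of section 11.9 is a minor note. Overall this is a defect in the wording of the primary safety decision rule that should be fixed, not evidence that the 9+3 design is unsound.

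**What to change.** In section 12.1:

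1. In step 5, replace the reference to Cohorts II and III with Cohort III alone.
2. State that steps 3 and 4 apply to each of Cohorts II, III and IV, so that step 6 also has its branches for one DLT and for two or more.
3. Restate the escalation probability at a 30% DLT rate as 9.4% (or as less than 10%).

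As a minor addition, the first sentence of section 11.9 should say what its stopping rule stops (the subject's dosing, the cohort or the trial) and how it relates to the steps in 12.1. That choice belongs to the sponsor.

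The cost is a short wording amendment. It adds no visits or procedures, and the maximum for escalation stays at 39.

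### The stated chance of under 9% of escalating at a 30% DLT rate does not hold for the three-patient run-in (up to 34.3%) and is narrowly missed at Cohort II (9.4%)

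*Combined protocol and SAP*

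**What the plan says.** Section 12.1 names safety as the primary statistical outcome and sets out a six-step escalation algorithm.

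- **Run-in (Cohort I, three patients, 50 mg), step 1:** "If no patient has a DLT observed by the cervix check visit after the last suppository, the trial will proceed to the next level".
- **Cohort II (nine patients, 200 mg, one cycle), steps 2 to 4:** escalate if no patient has a DLT. "If exactly one of the 9 patients has a DLT by Week 1-2 after the last suppository, three more patients will be enrolled", and escalation follows if none of those three has one. Two or more DLTs among the 9 or 12 stop escalation.
- **Cohort III (nine patients, 200 mg, two cycles), step 5:** "If no patient has a DLT observed in Cohorts II and III, then the dose level will be considered safe", and escalation follows.
- **Size:** "The maximum sample size for dose escalation is 39".

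On the algorithm's performance, with 30% as the rate in question, the section says: "there will be less than 9% probability to escalate to the next higher dose level if the DLT rate for the current dose level".

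Two other sections describe the run-in gate differently. Section 3.2: "dose escalation will only occur if no mucosal or systemic adverse events are reported in the first cohort of three subjects". Section 11.2: "If no local irritation or systemic toxicities observed in the first 3 patients at 50mg, the dosage will escalate".

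**The concern.** The under-9% figure is given once, for the algorithm as a whole. Step 1 of that algorithm is the run-in, Table 4 lists Cohort I among the levels, and nothing excepts it. A rule that needs only three DLT-free patients cannot give so small a chance of passing at a 30% DLT rate.

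The sentence is the plan's only quantitative statement about how well the design protects patients on its primary outcome. A reader who relies on it would think the run-in screens far better than it does. The run-in governs the fourfold step from 50 to 200 mg; later steps add cycles at the same dose. Section 3.1 acknowledges that no pharmacologic data have been published for intravaginal use.

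**Working it through.** **Inputs.** Cohort sizes and escalation rules come from Section 12.1 and Table 4. The DLT rate is the plan's own p = 0.30. Patients are treated as independent, so all figures are exact binomial.

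**The plan's figure.** The written rules do not reproduce it. A value below 9% does arise if 12 patients are always treated and at most one may have a DLT:

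0.7^12 + 12 × 0.3 × 0.7^11 = 0.0138 + 0.0712 = 0.0850.

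The written rule is looser because it escalates at 0 of 9 without treating the extra three. The difference is 0.7^9 × P(2 or more DLTs in 3) = 0.0404 × 0.216 = 0.0087. That this is where the stated figure came from is an inference.

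**Cohort I to II (0 of 3).** 0.7^3 = 0.343. A zero-DLT rule would need seven patients to fall below 9%: 0.7^6 = 0.118, 0.7^7 = 0.082. With three patients, the bound is met only if the DLT rate exceeds 1 − 0.09^(1/3) = 55.2%.

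**Cohort II to III (0 of 9, or 1 of 9 then 0 of 3; below, the 9+3 rule).**

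- 0 of 9: 0.7^9 = 0.0404
- 1 of 9, then 0 of 3: 9 × 0.3 × 0.7^8 × 0.7^3 = 0.0534
- Total: 0.0937

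This rule falls below 9% at a DLT rate of about 30.3%.

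**Cohort III to IV.** Two readings are possible.

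- If the 9+3 rule carries over, as the maximum of 39 (3 + 3 × 12) implies: 9.4%.
- If step 5 is read literally (no DLT in Cohorts II and III): at most 0.7^9 = 4.0%. If Cohort II also has a 30% rate and has just passed the 9+3 rule, it is (0.0404 / 0.0937) × 0.0404 = 1.7%.

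Cohort IV has no higher level.

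**Stricter run-in gate.** The documents give no rate for any mucosal or systemic event. Assumed per-patient rates of 40%, 50% and 60% give (1 − q)^3 = 21.6%, 12.5% and 6.4%.

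**Passing both I and II**, with a 30% rate at each: 0.343 × 0.0937 = 3.2%.

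**Other DLT rates:**

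| DLT rate | 0/3 rule | 9+3 rule |
|---|---|---|
| 10% | 72.9% | 67.0% |
| 20% | 51.2% | 28.9% |
| 30% | 34.3% | 9.4% |
| 40% | 21.6% | 2.3% |

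**The case against.** **The run-in gate may be stricter than zero DLTs.** Sections 3.2 and 11.2 would block escalation on milder events, and Section 5.0 also speaks of side effects short of a DLT. Under those gates 34.3% is a ceiling and the true value is unknown. This stands, and is why the figure is given as at most 34.3%. It does not rescue the sentence: the any-event rate would have to exceed about 55%, and Section 12.1 itself uses the DLT gate.

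**Section 11.9 could be read as stopping the trial at the first DLT.** Cohort II would then escalate only on 0 of 9, at 4.0%, within the bound. That reading contradicts step 3, which adds three patients after one DLT, and it leaves the run-in at 34.3%. The Cohort II figure therefore belongs to the 9+3 rule and should be labelled so.

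**The sentence may have been meant only for the nine-patient levels.** This is possible but not written, and the 9+3 rule itself gives 9.37%.

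**The consequences are limited.** This is fair. The sentence triggers no action. Passing both the run-in and Cohort II at a 30% rate has probability 3.2%, but the sentence speaks of the current level, not of two levels jointly. Section 3.1 reports no dose-limiting toxicity with intravenous doses up to 8 mg/kg, against at most 1 mg/kg in the run-in, so a 30% rate at 50 mg looks unlikely. The Cohort II gap of 0.4 percentage points would not change the design.

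**Conclusion.** The concern holds. At a 30% DLT rate, Section 12.1's rules give at most 34.3% for the run-in and 9.4% for Cohort II, against a stated bound of under 9%. Cohort III is 9.4% under the 9+3 rule, or at most 4.0% under step 5, which meets the bound. The run-in discrepancy is the material one.

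The figures assume independent patients and the DLT-based gates of Section 12.1; a stricter run-in gate could only lower the 34.3%. This is a misstated operating characteristic for the primary outcome. It should be corrected, but it does not show that the design itself is unsafe.

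**What to change.** Replace the sentence with text such as:

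> If the true DLT rate is 30%, the probability of escalating is at most 34.3% from the three-patient run-in (0/3 DLT) and 9.4% from a 200 mg level using the 9+3 rule (0/9, or 1/9 then 0/3).

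Two clarifications belong with it:

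1. State which run-in gate governs: no DLT (Section 12.1), or no mucosal or systemic event (Sections 3.2 and 11.2).
2. State whether Cohort III follows the 9+3 rule or step 5's zero-DLT rule. If step 5 governs, give at most 4.0% for that level.

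A small table of escalation probabilities at DLT rates of 10% to 40% would help but is optional.

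The cost is one sentence and two clarifications of rules already in the text. The stated protection becomes less favourable. Restating the figure changes no patient numbers or conduct.
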